5.2.1 If subjects withdraw before/during Week 48 due to		
5.2.1.1 Safety reasons (e.g. AE/death, liver chemistry stopping criteria, renal toxicity withdrawal criteria, QTc withdrawal criteria et al, as recorded in eCRF Conclusion form)	No virologic data at Week 48 Window	Disc due to AE/death
5.2.1.2 Non-safety related reasons (e.g. Lack of efficacy, protocol deviation, withdrew consent, loss to follow-up, study closed/terminated, investigator discretion et al, as recorded in eCRF Conclusion Form)		

 • Last on-treatment VL <50 c/mL OR no on-treatment VL available during study 	No virologic Data at Week 48 Window	Disc for other reasons

 • Last on-treatment VL ≥ 50 c/mL AND withdrawal due to Lack of efficacy 	HIV1-RNA ≥ 50	Disc. for lack of efficacy

 • Last on-treatment VL ≥ 50 c/mL AND withdrawal due to all other non-safety related reasons 	HIV1-RNA ≥ 50	Dis. for other reason while not below 50

a: Excluding permitted change in background therapy where change or decision to change is made prior to/on the first on-treatment viral result

Examples from FDA guidance

Data in Window

Virologic outcome should be determined by the last available measurement while the patient is on treatment and continued on trial within the time window:

- HIV-RNA = 580 copies/mL at Day 336, HIV-RNA below 50 copies/mL on Day 350. This should be categorized as HIV-RNA below 50 copies/mL.

No Data in Window

Discontinued study due to Adverse Event or Death:

- Any patient who discontinues because of an AE or death before the window should be classified as *Discontinued due to AE or Death* (as appropriate), regardless of the HIV-RNA result, even if the HIV-RNA is below 50 copies/mL at the time of discontinuation.
- However, if a patient has an HIV-RNA value in the time window and also discontinues in the time window, the viral load data should be used to classify the patient's response. This is the Virology First hierarchy:
 - a. HIV-RNA below 50 copies/mL at Day 336 and discontinues because of AE or even dies on Day 360 — this person is categorized as having HIV-RNA below 50 copies/mL.

- b. HIV-RNA is 552 copies/mL on Day 336 and the patient discontinues on Day 360, the patient is categorized as having HIV-RNA greater than or equal to 50 copies/mL.

Discontinued for Other Reasons:

- Only patients who have achieved virologic suppression can be counted as *Discontinued for Other Reasons*.
- If a patient discontinues the study before the time window because of *lack of efficacy* then the patient should be included in the HIV-RNA greater than or equal to 50 row and not in the Discontinued for Other Reasons row.
- If a patient discontinues because of *subject withdrew consent* and his or her HIV-1 RNA result at the time of discontinuation was equal to or above 50 copies/mL, then he or she should be categorized as HIV-RNA greater than or equal to 50 and NOT as Discontinued for Other Reasons.
- If a patient discontinued because of *Lost to Follow-Up* and the last HIV-RNA result was 49 copies/mL, then the patient can be categorized as Discontinued for Other Reasons.
- If patients changed background treatment — *not permitted by protocol*— they should be captured in the HIV-RNA greater than or equal to 50 copies/mL row.

On study but missing data in window:

- If there are no data during Days 294 to 377, but there is an HIV-RNA below 50 copies/mL on Day 380, this patient should be considered *On Study but Missing Data in Window*.

If there are no data during Days 294 to 377, but there is an HIV-RNA equal to or above 50 copies/mL on Day 280, this patient also should be classified as *On Study but Missing Data in Window*.

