7.1.5.1. Statistical Methodology Specification

Primary Statistical Analyses
Endpoint

 Proportion of Participants with Plasma HIV-1 ≥ 50 c/mL at Week 48 using the Snapshot algorithm for the ITT-E population. ‘HIV-1 RNA≥ 50’ are based on the Snapshot algorithm includes subjects who had plasma HIV-1 RNA ≥ 50 c/mL at Week 48, who discontinued for lack of efficacy, who discontinued for other reasons while not < 50 c/mL, or who changed ART).
Snapshot Dataset

 Virologic outcome (‘HIV-RNA < 50’ or ‘≥ 50 copies/mL’) per Snapshot algorithm is determined by the last available on-treatment HIV-1 RNA measurement within the analysis visit window of interest (please refer to analysis window defined in Table 11). In addition, subjects who discontinue for reasons not related to adverse event with on-treatment HIV-1 RNA result at the time of discontinuation ≥ 50 copies/mL or who change study treatment not permitted per protocol during maintenance phase before the analysis visit are classified as ‘HIV-RNA ≥ 50 copies/mL’. Full details of the Snapshot algorithm are provided in Section 13.11.
Model Specification

 The primary efficacy endpoint will be analysed using a stratified analysis with Cochran-Mantel-Haenszel (CMH) weights, adjusting Baseline third agent class (PI, INI, or NNRTI) and sex at birth The CMH estimate of the adjusted treatment difference will be calculated as a weighted average of strata-specific estimates of the treatment difference calculated within each of the following Baseline analysis strata resulting from the cross classification of both stratification factors: 
 Baseline third agent class PI AND Male sex at birth Baseline third agent class PI AND Female sex at birth Baseline third agent class INI AND Male sex at birth Baseline third agent class INI AND Female sex at birth Baseline third agent class NNRTI AND Male sex at birth Baseline third agent class NNRTI AND Female sex at birth If n_k is the number of CAB LA + RPV LA treated subjects, m_k is the number of the control arm treated subjects, and $N_k = n_k + m_k$ is the total number of subjects in the kth stratum, then the CMH estimate is given by $\hat{d}_{cmh} = \frac{\sum W_k \hat{d}_k}{\sum W_k}$ 
where

Primary Statistical Analyses

$$W_k = \frac{n_k m_k}{N_k}$$

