13.4.2. Treatment State

Within each treatment study phase (i.e. Maintenance and Extension—based on assignment of study phase described in Section 13.4.1), only those assessments which occur within the ranges shown in Table 20 will be considered ‘on-treatment’ for the given phase.

Table 20 Treatment State within Study Phases

Study Phase	Treatment State	Date Range
Screen	Pre-treatment	All assessments/events within phase
Maintenance	On-treatment	Current ART arm: Date \leq Maintenance Current ART Stop Date + 1
		IM Q4W arm: Date \leq max(Date of Last Q4W IM Dose + 35, Last Oral dose Date + 1);
	Post-treatment	Current ART arm: Date $>$ Current ART Stop Date + 1
		IM Q4W arm: Date $>$ max(Date of Last Q4W IM Dose + 35, Last Oral dose Date + 1)
Extension	On-treatment	Date \leq max(Date of Last Q4W IM Dose + 35, Last Oral dose Date + 1)
	Post-treatment	Date $>$ Date of Last Q4W IM Dose + 35, Last Oral dose Date + 1)
Long-Term Follow-up	On-treatment	Date \leq min(LTFU ART start date, max(Last Injection Date + 35, Last Oral dose Date + 1))
	Post-treatment	Date $>$ min(LTFU ART start date, max(Last Injection Date + 35, Last Oral dose Date + 1))

Note1: Treatment State is determined after data has been assigned to the study phases as defined in Section 13.4.1

Note2: Last Q4W IM / last oral dose/ Maintenance Current ART Stop Date is only applied to subjects who permanently discontinue from study treatment

Note3: Date = Assessment/Start Date.

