13.11. Appendix 11: Snapshot Algorithm Details

Detailed Algorithm Steps

- Consider an analysis visit window for Week X (e.g. Week4, ...Week 24, Week 48 et al). The Window for Week 24/48 visit is defined in Table 11 (e.g. window for Week 48 is ± 6 Week: $295 \leq \text{Study Day} \leq 378$) and in Table 9 for other visits through to Nominal Week 52 at Maintenance Phase. The Snapshot Analysis at post Maintenance Phase will not be appropriate because a large portion of responders will be switched to other studies and not all subjects would have the chance to reach same timepoint.
- The HIV1-RNA threshold of 50, 200 copies/mL will be analysed, respectively, in this study
- The analysis window 'Week 48' and HIV1-RNA threshold of '50 copies/mL' are used for the purpose of illustration. A subject's Snapshot response and reason at Week 48 are categorized as below.
 - HIV1-RNA < 50 copies/mL
 - HIV1-RNA ≥ 50 copies/mL
 - Data in window not below 50
 - Discontinued for lack of efficacy
 - Discontinued for other reason while not below 50
 - Change in background therapy*
 - No Virologic Data at Week 48 Window
 - Discontinued study due to AE or death
 - Discontinued study for other reasons
 - On study but missing data in window

* Note: since changes in ART are not permitted in this protocol, all such subjects who change ART during the maintenance phase will be considered 'HIV1-RNA ≥ 50 copies/mL'. if the change in ART is made prior to an analysis timepoint. Subjects with protocol permitted oral bridging treatment will not be considered ' HIV1-RNA ≥ 50 copies/mL' due to 'change in ART'.

- The steps in determining response and reasons are indicated in Table below, in the order stated.

Detailed steps		
Please note that the following scenarios will NOT be penalized Per Snapshot algorithm (i.e. please excluding these scenarios from Condition 1-4).		

 • Dose reduction, dropping a component, or change in formulation (e.g. 'Tivicay + Kivexa' to 'Triumeq' with the identical ingredients) 		
Condition ('Week 48' indicates Week 48 window)	Response	Reasons
1. If non-permitted change in background therapy prior to Week 48	HIV1-RNA ≥ 50	Change in background therapy
2.If permitted change ^[a] in background therapy prior to Week 48 AND the latest on-treatment VL prior to/on the date of change is ≥ 50 c/m (NA to this study)	HIV1-RNA ≥ 50	Change in background therapy

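### The SAP classifies a withdrawal for lack of efficacy in two ways in the primary endpoint: step 5.2.1.2 of Appendix 11 conflicts with the definition in Section 7.1.5.1

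*SAP*

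**What the plan says.** Appendix 11 tells the programmer how to apply its table: "The steps in determining response and reasons are indicated in Table below, in the order stated". For a participant with no viral load in the Week 48 window who withdrew before or during it, step 5.2.1.2 covers "Non-safety related reasons (e.g. Lack of efficacy, protocol deviation, withdrew consent, loss to follow-up" and further reasons. It has three rows:

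- "Last on-treatment VL <50 c/mL OR no on-treatment VL available during study": no virologic data, discontinued for other reasons. Lack of efficacy is not excepted.
- Last on-treatment value >=50 c/mL "AND withdrawal due to Lack of efficacy": HIV-1 RNA >=50, discontinued for lack of efficacy.
- Last on-treatment value >=50 c/mL and any other non-safety reason: HIV-1 RNA >=50.

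The endpoint definition in Section 7.1.5.1 counts as HIV-1 RNA >=50 those "who discontinued for lack of efficacy, who discontinued for other reasons while not < 50 c/mL". The viral-load condition there belongs to the other reasons, not to lack of efficacy. The guidance example later in Appendix 11 says that a patient who discontinues before the window for lack of efficacy "should be included in the HIV-RNA greater than or equal to 50 row and not in the Discontinued for Other Reasons row".

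Appendix 15 makes withdrawal for lack of efficacy an event in both Kaplan-Meier analyses (TRDF and ERDF), whatever the viral load.

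Other text follows the step table's logic. Section 7.1.4, the Snapshot Dataset bullet in Section 7.1.5.1 and Section 13.6.4 classify non-AE discontinuations by the viral load at discontinuation and do not treat lack of efficacy separately.

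**The concern.** The primary endpoint is a failure count, and one kind of participant is a failure under the definition but a non-failure under the steps that implement it. Section 13.6.4 uses the whole analysis population as the denominator. A participant sent to the no-virologic-data category therefore leaves the numerator but stays in the denominator, and so counts as a non-failure.

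The same person would be an efficacy failure in the ERDF analysis and a non-failure in the primary analysis. Unless this is settled beforehand, the classification depends on which part of the SAP the programmer follows. With few expected failures and a 6% margin, a handful of participants can matter. Section 13.14 applies the same data handling to the IDMC work, so the rule also reaches the Week 24 futility Snapshot.

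**Working it through.** **1. Where the rules differ.** Take a participant withdrawn for lack of efficacy, with no viral load in the Week 48 window and no non-permitted ART change that an earlier step would already count as >=50.

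| Last on-treatment viral load | Step 5.2.1.2 | Section 7.1.5.1 definition and guidance example |
|---|---|---|
| >=50 c/mL | HIV-1 RNA >=50 | HIV-1 RNA >=50 |
| <50 c/mL | No virologic data | HIV-1 RNA >=50 |
| None | No virologic data | HIV-1 RNA >=50 |

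They differ in two cells, and in both the step table gives the lower failure count.

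**2. Whether the cells can be reached.** Under Table 20 (Section 13.4.2), once a participant on the injections stops permanently, values count as on-treatment up to "max(Date of Last Q4W IM Dose + 35, Last Oral dose Date + 1"). A rebound first measured after that limit is ignored and an earlier value <50 stands. In the control arm the limit is the ART stop date + 1 day, so a rebound first measured two or more days after stopping is ignored in the same way. For the third cell, Table 17 assigns Day 1 values to screening, so a withdrawal before any post-baseline sample leaves no on-treatment value.

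**3. Inputs for size.** The design is 570 randomised 1:1 (Section 2.3), so n = 285 per arm. The margin is 6% on the upper 95% limit (Section 5.5.1). The SAP gives no figure for this specific point. As a check on the inputs, six cells of Table 22 were recomputed by the beta-binomial predictive probability, with 143 of 285 per arm at the interim. The injectable/comparator failure counts 7/0, 7/4, 10/5, 9/3, 14/8 and 8/6 gave 17.3, 68.5, 29.1, 21.8, 13.3 and 72.5, all equal to the stated values.

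**4. Effect of one participant.** 1/285 = 0.35 percentage points on the failure rate of that arm.

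**5. Effect on the limit.** All failure counts from here on are assumptions. With x1 failures on the injections and x0 on control:

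d = x1/n − x0/n; upper limit = d + 1.96 × √[p1(1−p1)/n + p0(1−p0)/n].

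- 14 vs 4: p1 = 4.912%, p0 = 1.404%, d = 3.51%, SE = 1.458 points. Upper limit = 3.51 + 2.86 = 6.37%. Non-inferiority is not shown.
- 12 vs 4 (two of the 14 moved to no virologic data): p1 = 4.211%, d = 2.81%, SE = 1.379 points. Upper limit = 2.81 + 2.70 = 5.51%. Non-inferiority is shown.

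**6. Sensitivity to the assumed counts.**

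- From 12 vs 6 (upper limit 4.97%), two more failures on the injections give 5.82% and three more give 6.24%.
- From 6 vs 6 (2.36%), even five more on the injections give only 4.54%.
- From 12 vs 6, three more on control (12 vs 9) lower the limit to 4.14%.

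These are unadjusted Wald limits. The planned interval is the CMH estimate with the Sato variance, so the exact tipping points would shift somewhat.

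**The case against.** The step table is not an isolated slip. Section 7.1.4, the Snapshot Dataset bullet and Section 13.6.4 share its viral-load logic, and Section 7.1.5.1 sends the reader to Appendix 11 for full details. This shows that two readings run through the SAP. It does not remove the conflict, because the two places that name lack of efficacy outright both count it without a viral-load condition. Section 13.6.4 describes only what typically happens and itself defers to Appendix 11.

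The affected cases are also narrow. A participant whose rebound is first seen at an on-schedule injection visit has an on-treatment value >=50 and is counted correctly. On the injections, the case needs a first high value more than 35 days after the last injection, no oral bridging and no further injection, no viral load in the window, and a recorded reason of lack of efficacy. The cell with no on-treatment value is close to empty. All of this stands and limits the likely number.

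The Kaplan-Meier analyses and the listings of withdrawal reasons and viral loads would make such cases visible, and the <50 c/mL key secondary endpoint is unaffected. That is also correct, but none of it settles the primary classification.

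A reader might infer that failures are lost mainly on the injections and that the comparison is therefore biased towards non-inferiority. The SAP does not support that. The control arm's one-day allowance after stopping is shorter than 35 days and can produce the same case. Nothing in the SAP shows which arm would have more.

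**Conclusion.** The contradiction is established from the text alone: the SAP gives two results for the same participant in its primary endpoint, and one of them is a result that its own guidance example rules out. The step table can only lower the failure count of the arm in which the case occurs. The net direction across arms is unknown, and the number of cases is not given and is probably small. The example that changes the conclusion shows only that two participants could matter if the result lies near the margin; it does not predict that it will. On that basis this should be fixed before unblinding, but it does not show that the primary analysis is biased in a particular direction.

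**What to change.** Before unblinding:

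- In step 5.2.1.2, test lack of efficacy first and without a viral-load condition, with the result HIV-1 RNA >=50, discontinued for lack of efficacy.
- Restrict the row for a last value <50 or no on-treatment value to the other non-safety reasons.
- Align Section 7.1.4, the Snapshot Dataset bullet in Section 7.1.5.1 and Section 13.6.4 with this. Changing the table alone would leave the SAP inconsistent.

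If the viral-load condition on lack of efficacy is intended, the SAP should instead say so as a deliberate departure, change the endpoint definition to match, and add a sensitivity analysis that counts these withdrawals as failures.

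The cost is a few text edits and one program condition. The failure count may rise slightly in either arm.

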13.12. Appendix 12: Abbreviations & Trade Marks

13.12.1. Abbreviations

Abbreviation	Description
ADaM	Analysis Data Model
AE	Adverse Event
BMD	Bone Mineral Density
BMI	Body Mass Index
CAB	Cabotegravir
CDISC	Clinical Data Interchange Standards Consortium
CI	Confidence Interval
CMH	Cochran-Mantel-Haenszel
CPMS	Clinical Pharmacology Modelling & Simulation
CS	Clinical Statistics
CSR	Clinical Study Report
C-SSRS	Columbia Suicide Severity Rating Scale
CTR	Clinical Trial Register
CV _b	Coefficient of Variation (Between)
CV _b / CV _w	Coefficient of Variation (Between) / Coefficient of Variation (Within)
CVD	Cardiovascular Disease
CVF	Confirmed Virologic Failure
DAIDS	Division of AIDS
DBF	Database Freeze
DBR	Database Release
DOB	Date of Birth
DP	Decimal Place
DTG	Dolutegravir
eCRF	Electronic Case Record Form
eGFR	Estimated Glomerular Filtration Rate
EMA	European Medicines Agency
ERDF	Efficacy Related Discontinuation Failure
ESP	Extension Switch Population
FDA	Food and Drug Administration
FDAAA	Food and Drug Administration Amendments Act
FSFV	First Subject First Visit
GSK	GlaxoSmithKline
GUI	Guidance
HBV	Hepatitis B Virus
HCV	Hepatitis C Virus
HIV	Human Immunodeficiency Virus
HSR	Hypersensitivity Reaction
IA	Interim Analysis
ICH	International Conference on Harmonisation
IDMC	Independent Data Monitoring Committee

IDSL	Integrated Data Standards Library
IMMS	International Modules Management System
INI	Integrase Inhibitors
IP	Investigational Product
ITT	Intent-To-Treat
ITT-E	Intent-To-Treat Exposed
LOCF	Last Observation Carries Forward
MMRM	Mixed Model Repeated Measures
NCEP	National Cholesterol Education Program
NNRTI	Non-Nucleoside Reverse Transcriptase Inhibitors
NQ	Non Quantifiable
NRTI	Nucleoside Reverse Transcriptase Inhibitors
OC	Observed Case
PCI	Potential Clinical Importance
PD	Pharmacodynamic
PDMP	Protocol Deviation Management Plan
PI	Protease Inhibitors
PK	Pharmacokinetic
PopPK	Population PK
PP	Per Protocol
QC	Quality Control
QTcF	Frederica's QT Interval Corrected for Heart Rate
QTcB	Bazett's QT Interval Corrected for Heart Rate
RAMOS	Randomisation & Medication Ordering System
RAP	Reporting & Analysis Plan
RPV	Rilpivirine
SAE	Serious Adverse Event
SAC	Statistical Analysis Complete
SD	Standard Deviation
SDAC	Statistics Data Analysis Centre
SDTM	Study Data Tabulation Model
SOP	Standard Operation Procedure
TA	Therapeutic Area
TFL	Tables, Figures & Listings
TRDF	Treatment Related Discontinuation Failure

13.12.2. Trademarks

Trademarks of the GlaxoSmithKline Group of Companies
Dolutegravir
Triumeq

Trademarks not owned by the GlaxoSmithKline Group of Companies
NONMEM
Rilpivirine
SAS
WinNonlin

13.13. Appendix 13: List of Data Displays

13.13.1. Data Display Numbering

The following numbering will be applied for RAP generated displays:

Section	Tables	Figures
Study Population	1.01 to 1.n	1.01 to 1.n
Efficacy	2.01 to 2.n	2.01 to 2.n
Safety	3.01 to 3.n	3.01 to 3.n
Pharmacokinetic	4.01 to 4.n	4.01 to 4.n
Pharmacokinetic / Pharmacodynamic	5.01 to 5.n	5.01 to 5.n
Health Outcomes	6.01 to 6.n	6.01 to 6.n
Virology	7.01 to 7.n	7.01 to 7.n
Section	Listings	
ICH Listings	1 to x	
Other Listings	y to z	

13.13.2. Mock Example Shell Referencing

Non IDSL specifications will be referenced as indicated and if required an example mock-up displays provided a separate document.

13.13.3. Deliverables

Delivery ^[1]	Description
IDMC_CVF monitoring	Refer to IDMC Charter, Section 12.3, Appendix C
IDMC_Futility at Week 24	Refer to IDMC Charter, Section 12.3, Appendix C
IDMC_Futility adhoc	Refer to file-note IDMC Adhoc Analysis
HL	Headline at Week 48
WK48	Week 48
WK96	Week 96
EOS	End of study

NOTES:

1. Indicates priority (i.e. order) in which displays will be generated for the reporting effort.

13.13.4. Study Population Tables

Study Population Tables					
No.	Population	IDSL / TST ID / Example Shell	Title	Programming Notes	Deliverable
Subject Disposition					
1.1.	All Subjects Screened	SP1	Summary of Study Populations	CS CORE	WK48, 96, EOS
1.2.	All Subjects Screened	Shell TSP1	Summary of Subjects by country and investigator		WK48, 96, EOS
1.3.	All Subjects Screened	ES6	Summary of Screening Status and Reasons for Screening Failures	CS CORE	WK48, 96, EOS
1.4.	ITT-E	EudraCT age	Summary of Age Categories	CS CORE	WK48, 96, EOS
1.5.	ITT-E	ES1	Summary of Subject Accountability: Study Conclusion Record – ITT-E	ICH E3, GSK CTR, FDAAA, EudraCT	WK48, 96, EOS
1.6.	ITT-E	ES1	Summary of CAB+RPV Discontinuation for randomized Q4W Arm	CS CORE	WK48, 96, EOS
1.7.	ITT-E	ES1	Summary of Subject Accountability: Maintenance Phase Conclusion Record – ITT-E	ICH E3, GSK CTR, FDAAA, EudraCT	HL, WK48
1.8.	ESP	ES1	Summary of CAB+RPV Discontinuation for Randomized Current ART Arm during Extension Phase	CS CORE	WK48, 96, EOS

Study Population Tables					
No.	Population	IDSL / TST ID / Example Shell	Title	Programming Notes	Deliverable
1.9.	LTFU	ES1	Summary of Subject Accountability: Long-term follow up Phase Conclusion Record – LTFU	ICH E3, GSK CTR, FDAAA, EudraCT	WK48, 96, EOS
1.10.	ITT-E	HIV_ES1	Summary of Subject Accountability: Withdrawals by Visit at Maintenance phase		WK48
1.11.	ITT-E	HIV_ES1	Summary of Subject Accountability: Maintenance+extension phase Conclusion Record	For Q4W arm only	WK48, 96, EOS
1.12.	ESP	HIV_ES1	Summary of Subject Accountability: Extension phase Conclusion Record	For Current art arm only	WK48, 96, EOS
1.13.	ITT-E	DV1	Summary of Important Protocol Deviations (Maintenance phase)	CS CORE, At wk96, Maintenance+extension phase for those Q4W IM arm; and Extension phase only for ESP,	WK48
1.14.	ITT-E	SA2	Summary of Protocol Deviations Leading to Exclusion from the Per-Protocol Population (Maintenance phase)	CS CORE	WK48
1.15.	ITT-E	IE1	Summary of Inclusion/Exclusion Criteria Deviations		WK48, 96, EOS
Demography and Baseline					
1.16.	ITT-E	Shell TSP2	Summary of Demographic Characteristics	See also DM1 in IDSL	HL, WK48, 96, EOS
1.17.	ITT-E	DM5	Summary of Race and Racial Combinations	CS CORE	WK48, 96, EOS
1.18.	ITT-E	DM6	Summary of Race and Racial Combinations Details	CS CORE	WK48, 96, EOS
1.19.	ITT-E	Shell TSP3	Summary of Hepatitis Status at Entry		WK48, 96, EOS
1.20.	ITT-E	CDC1	Summary of Derived CDC Stages of HIV Infection at Baseline		WK48, 96, EOS
1.21.	ITT-E	Shell TSP4	Summary of Baseline Cardiovascular Risk Assessments		WK48, 96, EOS
1.22.	ITT-E	Shell TSP5	Distribution of CD4+ Cell Count Results at Screening and Baseline		WK48, 96, EOS

Study Population Tables					
No.	Population	IDSL / TST ID / Example Shell	Title	Programming Notes	Deliverable
Medical Conditions, Concomitant Medications & Antiretroviral Therapy					
1.23.	ITT-E	MH1	Summary of Current Medical Conditions	CS CORE	WK48, 96, EOS
1.24.	ITT-E	MH1	Summary of Past Medical Conditions	CS CORE	WK48, 96, EOS
1.25.	ITT-E	MH4	Summary of Current Cardiac, Gastrointestinal, Metabolism and Nutrition, Psychiatric, Renal and Urinary, Nervous System Conditions, and Hepatobiliary disorders		WK48, 96, EOS
1.26.	ITT-E	MH4	Summary of Past Cardiac, Gastrointestinal, Metabolism and Nutrition, Psychiatric, Renal and Urinary, Nervous System Conditions, and Hepatobiliary disorders		WK48, 96, EOS
1.27.	ITT-E	CM8	Summary of Concomitant Medication Ingredient Combinations (Maintenance phase)	At wk96/EOS, Maintenance+extension phase for those Q4W IM arm; and Extension phase only for ESP ,	WK48, 96, EOS
1.28.	ITT-E	Shell TSP6	Summary of Antiretroviral Therapy stopped prior to Screening		WK48, 96, EOS
1.29.	ITT-E	Shell TSP7	Summary of Antiretroviral Therapy Taken during Screening		WK48, 96, EOS
1.30.	ITT-E	TSP11	Summary of Antiretroviral Regimen Taken during Screening		WK48, 96, EOS
1.31.	ITT-E	Shell TSP7a	Time Since First Antiretroviral Therapy until Maintenance Phase Start		WK48, 96, EOS
1.32.	ITT-E	Shell TSP8	Summary of Baseline third agent class		HL, WK48, 96, EOS
1.33.	ITT-E	Shell TSP9	Summary of Lipid Modifying Agent Use at Baseline		WK48, 96, EOS
1.34.	ITT-E	Shell TSP10	Summary of Lipid Modifying Agent Use Starting Post-Baseline (Maintenance phase))		WK48, 96, EOS
1.35.	ITT-E	SU1	Summary of Substance use		WK48, 96, EOS
1.36.	ITT-E	Shell TSP12	Summary of HIV Risk Factor		WK48 96, EOS

